8.4.5 ADVERSE EVENT REPORTING

All AEs, as defined above, will be collected and reported. Data collection will occur via electronic spreadsheet. The information will be saved in REDCap and managed by the study team at each site. In consultation with the PI, a trained member of the study team will be responsible for conducting an evaluation of a SAE and shall report the results of such evaluation to the NIH and the reviewing Institutional Review Board (IRB) as soon as possible and in accordance with the reviewing IRB policy

8.4.6 SERIOUS ADVERSE EVENT REPORTING

In consultation with the PI, a trained member of the study team will be responsible for conducting an evaluation of a SAE and shall report the results of such evaluation to the NIH and the reviewing IRB as soon as possible and in accordance with the reviewing IRB policy.

8.4.7 REPORTING EVENTS TO PARTICIPANTS

N/A

8.4.8 EVENTS OF SPECIAL INTEREST

N/A

8.4.9 REPORTING OF PREGNANCY

N/A

8.5 UNANTICIPATED PROBLEMS

8.5.1 DEFINITION OF UNANTICIPATED PROBLEMS

This protocol uses the definition of Unanticipated Problems (UPs) as defined by the Office for Human Research Protections (OHRP). OHRP considers unanticipated problems involving risks to participants or others to include, in general, any incident, experience, or outcome that meets all of the following criteria:

- Unexpected in terms of nature, severity, or frequency given (a) the research procedures that are described in the protocol-related documents, such as the IRB-approved research protocol and informed consent document; and (b) the characteristics of the participant population being studied;
- Related or possibly related to participation in the research (“possibly related” means there is a reasonable possibility that the incident, experience, or outcome may have been caused by the procedures involved in the research); and
- Suggests that the research places participants or others at a greater risk of harm (including physical, psychological, economic, or social harm) than was previously known or recognized.

8.5.2 UNANTICIPATED PROBLEMS REPORTING

The investigator will report UPs to the reviewing IRB and to the lead PI. The UP report will include the following information:

- Protocol identifying information: protocol title and number, PI's name, and the IRB project number
- A detailed description of the event, incident, experience, or outcome
- An explanation of the basis for determining that the event, incident, experience, or outcome represents an UP
- A description of any changes to the protocol or other corrective actions that have been taken or are proposed in response to the UP

To satisfy the requirement for prompt reporting, UPs will be reported using the following timeline:

- UPs will be reported to the IRB and to the National Cancer Institute (NCI) in accordance with policy regarding timeliness of reporting
- All UPs should be reported to appropriate institutional officials (as required by an institution's written reporting procedures), the supporting agency head (or designee), and the OHRP in accordance with policy regarding timeliness

8.5.3 REPORTING UNANTICIPATED PROBLEMS TO PARTICIPANTS

N/A

9 STATISTICAL CONSIDERATIONS

9.1 STATISTICAL HYPOTHESIS

We hypothesize that, compared with patients randomized to AC, patients randomized to the BRIGHT intervention will have reduced BID as measured by change in the IMAGE-HN score of ≥ 9 from baseline to 6-months follow-up. Alternatively, our null hypothesis is that BRIGHT will not improve BID relative to AC, as measured by change in the IMAGE-HN score of < 9 from baseline to 6-months follow-up.

9.2 SAMPLE SIZE DETERMINATION

The primary endpoint for the proposed RCT is the change in the IMAGE-HN score from baseline to 6-month follow-up. Our primary objective is to test the hypothesis that BRIGHT decreases HNC-related BID from baseline to 6-month follow-up (as measured by clinically significant reduction in the IMAGE-HN score) relative to AC. We target a mean difference in IMAGE-HN score reduction of 9 between BRIGHT and AC at 6 months. This targeted difference is (1) clinically important using widely accepted distribution-based methods of patient reported outcome measure interpretation⁸⁸ and (2) commensurate with clinically meaningful differences in BID among cancer survivors from other appropriately powered trials.^{14,41,100} In our pilot RCT, at 3-months post-intervention (a timepoint similar to 6 month follow-up), BRIGHT improved IMAGE-HN scores from baseline relative to AC (mean model-based difference in change in IMAGE-HN score = -17.1 [90% CI, -25.6 to -8.6] points; $P = 0.002$). The targeted clinically important difference in IMAGE-HN score reduction of 9 thus appears highly feasible. Determining the sample size for the proposed RCT requires adjusting for the clustering of trial participants within psychologist (BRIGHT arm) or HN clinical staff member (AC arm). We expect the number of clusters in each arm to be 9 with an average of 10 trial participants per cluster. We further estimate an intra-class correlation coefficient (ICC) = 0.05^{101,102} and standard deviation = 16 based on similar studies.^{41,100} Given these assumptions, a sample size of $N = 180$ ($n = 90/\text{arm}$) yields 83.7% power to detect the targeted 9-point average reduction in IMAGE-HN scores between the BRIGHT and AC arms with two-sided $\alpha = 0.05$ (PASS v 08.0.13, Inequality Tests for Two Means in a Cluster-Randomized Design module).

Targeting an attrition rate = 20%, we plan to enroll 226 HNC survivors with BID to achieve our target sample size of $N = 180$ evaluable patients for the modified intention-to-treat (ITT) analyses of the efficacy population. In our pilot RCT, 20% (11/54) of eligible patients who accrued to the RCT were not evaluable for the primary endpoint: $n = 7$ (13%) went off study per protocol due to the development of recurrent HNC or a second non-HNC malignancy; and $n = 3$ (7%) withdrew due to intercurrent physical demands. No patients were lost to follow-up.

9.3 POPULATIONS FOR ANALYSES

The **safety analysis set** (SAS) is composed of all patients enrolled who receive any part of either the BRIGHT or AC intervention. The SAS will be used to conduct all safety analyses. Patients will be analyzed based on the intervention received regardless of the assignment at randomization.

The **6-month IMAGE-HN evaluable set** is composed of all patients enrolled in the trial who have completed the baseline and 6-month follow-up IMAGE-HN survey instrument. Analysis will be performed based on assignment at randomization regardless of the intervention received (modified intent to treat). This analysis set will be used for analysis of the primary endpoint.

Analysis sets for secondary endpoints specific to PROMs at a given follow-up timepoint will be defined as the set of trial participants who have completed both the baseline and the follow-up survey at the specified timepoint. Analysis will be performed based on assignment at randomization regardless of the

intervention received (modified intent to treat). These analysis sets will be used for analysis of the secondary endpoints (**Table 5**).

The **full analysis set (FAS)** is the set of all trial participants who enroll and are eligible for the study. Patients who enroll but subsequently drop out prior to receiving any of the assigned intervention will be replaced. This analysis set will be used for secondary analyses of both the primary endpoint and secondary endpoints.

Per protocol set is composed of all patients enrolled in the trial who have completed 6-weeks of the BRIGHT/AC interventions as described in the protocol. This analysis set will be used for secondary analyses of both the primary endpoint and secondary endpoints.

Details about the analytic plan for each population are described in detail in **Section 9.4**.

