2.3 RISK/BENEFIT ASSESSMENT

2.3.1 KNOWN POTENTIAL RISKS

Overall, this research study poses no more than minimal risks to participants. The single-arm pilot study of BRIGHT and single-site pilot RCT comparing BRIGHT with AC were minimal risk studies that were approved by the Medical University of South Carolina (MUSC) Institutional Review Board (IRB) under an expedited review (45CFR46.110). The proposed study will use a single IRB structure with MUSC serving as the IRB of record. No formal Data and Safety Monitoring Board was required in the prior studies of BRIGHT, although a Data and Safety Monitoring Plan (DSMP) with principal investigator (PI) and IRB-based oversight was created. The main study procedures include (1) either BRIGHT (CBT) or AC (a manualized tele-supportive care intervention that controls for professional attention, dose, delivery method, and common factors) and (2) completion of study questionnaires. These are generally considered minimal risk activities, although one of the questionnaires inquires about suicidal ideation. There are no physical, financial, legal, social, or cultural, risks to the study participants by joining this study. The primary risks of the study associated with the intervention or study assessments include psychological/emotional distress and breach of privacy/confidentiality.

Psychological/emotional distress: Subjects may experience adverse psychological reactions such as anxiety, depression, stress, distress, or suicidal ideation as a result of discussing issues related to cancer, body image, stigmatization, isolation, coping strategies, or social support. These issues may occur during the completion of study questionnaires (baseline or post-treatment) or during the intervention (BRIGHT or AC). However, based on our experience with prior similar trials, we expect only minimal risk to participants. Nevertheless, we have a specific protocol to address situations in which a patient becomes distressed as a result of either the study intervention or study assessments. The project coordinator and all of the study interventionists have extensive experience dealing with this patient population and appropriate safeguards have been put in place to mitigate against this risk in either situation. There is a licensed clinical psychologist at each site that is trained in assessing and intervening upon distress.

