8.4 ADVERSE EVENTS AND SERIOUS ADVERSE EVENTS

8.4.1 DEFINITION OF ADVERSE EVENTS

This trial is considered to carry a low risk to subjects (i.e. has a "no more than minimal risk" designation). As such, this protocol defines an adverse event (AE) as any sustained undesirable psychological, social, or emotional reaction that is definitely, probably, or possibly related to the study intervention. AEs include suicide attempt, sustained emotional distress, sustained depression, or other sustained mental health deterioration. This definition of an adverse event follows best practices for recording adverse events during psychological treatments.⁹⁹

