8.4.2 DEFINITION OF SERIOUS ADVERSE EVENTS

A serious adverse event (SAE) will be defined as any sustained undesirable psychological or mental health condition which is fatal, is life-threatening, requires or prolongs inpatient hospitalization, results in persistent or significant disability/incapacity, is medically significant and which the investigator regards as serious based on appropriate medical judgment that is directly due to a study intervention. An important medical event is any AE that may not result in death, be life-threatening, or require hospitalization but may be considered an SAE when, based upon appropriate medical judgment, it may jeopardize the patient and may require medical or surgical intervention to prevent one of the outcomes listed in the definitions of SAEs.

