8.4.3.2 RELATIONSHIP TO STUDY INTERVENTION/EXPERIMENTAL MANIPULATION

All AEs will have their relationship to study procedures, including the intervention, assessed by the PI based on temporal relationship and his clinical judgment. The degree of certainty about causality will be graded using the categories below.

- **Definitely Related** – There is clear evidence to suggest a causal relationship, and other possible contributing factors can be ruled out. The clinical event, including an abnormal laboratory test result, occurs in a plausible time relationship to study procedures administration and cannot be explained by concurrent disease or other drugs or chemicals. The response to withdrawal of the study procedures should be clinically plausible. The event must be pharmacologically or phenomenologically definitive.
- **Probably Related** – There is evidence to suggest a causal relationship, and the influence of other factors is unlikely. The clinical event, including an abnormal laboratory test result, occurs within a reasonable time after administration of the study procedures, is unlikely to be attributed to concurrent disease or other drugs or chemicals, and follows a clinically reasonable response on withdrawal.
- **Possibly Related** – There is some evidence to suggest a causal relationship (e.g., the event occurred within a reasonable time after administration of study procedures). However, other factors may have contributed to the event (e.g., the participant's clinical condition, other concomitant events). Although an AE may rate only as "possibly related" soon after discovery, it can be flagged as requiring more information and later be upgraded to "probably related" or "definitely related", as appropriate.

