8.4.4 TIME PERIOD AND FREQUENCY FOR EVENT ASSESSMENT AND FOLLOW-UP

Recording/reporting of AEs will begin after the subject signs informed consent and end after the subject completes the intervention and follow up period as defined in the protocol. AEs may be reported by the patient via self-report, noted in the electronic medical record, or reported directly by study personnel.

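### The protocol names distress from the study assessments as a primary risk, but its AE definition covers only the intervention and its safety set leaves out patients who never start a session

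*Protocol*

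**What the plan says.** Three places in the protocol take a wide view of harm.

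- Section 2.3.1: "The primary risks of the study associated with the intervention or study assessments include psychological/emotional distress and breach of privacy/confidentiality". On timing it adds: "These issues may occur during the completion of study questionnaires (baseline or post-treatment) or during the intervention (BRIGHT or AC").
- Section 8.4.4: "Recording/reporting of AEs will begin after the subject signs informed consent".
- Section 8.4.3.2: "All AEs will have their relationship to study procedures, including the intervention, assessed by the PI".

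Five places take a narrow view.

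- Section 8.4.1 defines an AE as a sustained psychological, social or "emotional reaction that is definitely, probably, or possibly related to the study intervention".
- Section 8.4.2 requires, for a serious event, a condition "that is directly due to a study intervention".
- Section 8.4.5 collects and reports the AEs that meet the foregoing definition.
- Section 9.4.4 summarizes AEs and SAEs by their relationship to a study intervention.
- Section 9.3 says that the safety analysis set "is composed of all patients enrolled who receive any part of either the BRIGHT or AC intervention. The SAS will be used to conduct all" analyses of safety.

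Section 9.3 also foresees patients who leave before receiving any of their assigned intervention: under the full analysis set, it says they are to be replaced.

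**The concern.** The protocol identifies two sources of distress, the sessions and the questionnaires, but its event definition and safety summaries are built around the first only. The baseline battery is completed after consent and before randomization (6.3) and includes a suicidal ideation scale (Table 1). AE recording is open during that window, yet no intervention has been delivered to which an event could be related.

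At stake is whether the trial's safety results can speak to a harm that the protocol itself lists. The protocol describes participation as carrying no more than minimal risk (2.3.1, 8.4.1). A safety table that has no defined place for assessment-related events cannot support that description for the assessment part of participation. There is also a consistency problem. Staff who follow 8.4.1 and staff who take their cue from 8.4.3.2 could treat the same event differently.

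**Working it through.** No figure in the plan depends on this point, so the check is a comparison of the rules, applied to each stretch of a patient's time on study. The order of events in 6.3 is consent, baseline questionnaires, randomization, then sessions.

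1. **Consent to randomization.** Recording is open (8.4.4) and the baseline battery is a named source of distress (2.3.1). No arm has been assigned and no session given, so on the literal wording of 8.4.1 a reaction cannot be even possibly related to the intervention. It is not an AE.
2. **Randomization to session 1.** The same holds for a reaction to the baseline battery. If the patient then leaves without a session, 9.3 puts that patient outside every safety analysis, even if the event was recorded.
3. **After session 1, reaction due solely to a questionnaire.** The patient is in the safety set, but the event does not meet 8.4.1.
4. **After session 1, cause mixed or uncertain.** The threshold in 8.4.1 reaches down to possible relatedness, and 8.4.3.2 allows that category where other factors may have contributed. A sustained reaction in a treated patient can therefore be an AE and be counted.

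Does 8.4.3.2 rescue the first three cases? It grades the relationship of AEs, which are events that 8.4.1 has already admitted. It does not admit new ones. Even if it were applied as the admitting rule, 9.4.4 would still report relationship to the intervention only, and 9.3 would still leave out patients who never start.

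Does unanticipated-problem reporting (8.5) rescue them? It covers events related to taking part in the research, but all its criteria must be met. One is that the event be unexpected given the procedures described in the protocol. Because 2.3.1 describes questionnaire distress, ordinary cases would generally fail that test. These reports are also not an input to 9.4.4.

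**Size.** The document does not give the number of patients who leave before session 1. The pilot's 6% (3 of 54, section 2.2.9) is dropout over the whole study, not dropout before a first session, so it cannot supply the number. The following is illustration only, with assumed never-start fractions applied to the planned enrolment of 226 (9.2):

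- 2%: 226 × 0.02 = 4.5 outside the safety set, 221.5 inside
- 5%: 226 × 0.05 = 11.3 outside, 214.7 inside
- 10%: 226 × 0.10 = 22.6 outside, 203.4 inside

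At any of these values most patients stay in the safety set. The 8.4.1 definition applies to everyone, so it is the main cause of the gap and the safety set is the smaller one.

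**The case against.** The strongest reply has four parts.

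**Events in treated patients can be counted.** This stands in full. A reader might infer that assessment distress is reported as zero by construction, or that none of 226 × 5 = 1,130 questionnaire occasions (baseline and 2, 3, 6 and 9 months) could yield an AE. The document does not support either inference. Four of the five occasions come after randomization, and for a treated patient a sustained reaction judged possibly related to the intervention qualifies. Only reactions due solely to a questionnaire are shut out, most clearly at baseline.

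**Other parts of the protocol notice distressed patients.** Section 2.3.3 has real-time flags for endorsed suicidal ideation and a response procedure for other distress. Section 7.2 records the date and reason for withdrawal. Section 9.5.7 has a monthly aggregate review that includes early withdrawals, and depression, anxiety and suicidal ideation scores are secondary endpoints. So these patients are not invisible. But none of these routes feeds the 9.4.4 summaries.

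**A safety set of treated patients is conventional, and a supplementary listing could be left to the SAP.** The first half stands, and the set should stay. The second half is weaker. The AE definition decides what sites collect, and a SAP cannot list events that were never recorded as AEs. Section 9.3 also already assigns all safety analyses to this set.

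**The definition was deliberately updated, counts only sustained reactions, and past use of these measures gave no undue distress (2.3.3).** This limits how many events to expect. Transient upset would not be an AE under either scope of relatedness. It does not explain why 2.3.1, 8.4.3.2 and 8.4.4 use a wider scope than 8.4.1. It also means there is no support for supposing that patients who leave early are those most harmed by the assessments. The reason given for pilot withdrawals is intercurrent physical demands (5.5.5).

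**Conclusion.** The point holds as a conflict between stated rules. Sections 2.3.1, 8.4.3.2 and 8.4.4 cover assessments and study procedures from consent onward. Sections 8.4.1, 8.4.2, 8.4.5 and 9.4.4 cover the intervention only, and 9.3 cuts off patients who receive none of it. Followed literally, two kinds of event are missing from the safety results: sustained reactions due solely to a questionnaire, and any event in a patient who never starts a session.

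The conclusion rests on reading 8.4.1 as the rule that admits events and 8.4.3.2 as a rule that only grades them, which is what the wording says. If sites instead treated 8.4.3.2 as the admitting rule, the first kind would be collected in treated patients, but the second would still be lost.

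The number of patients affected is unknown and probably modest. Efficacy inference is not touched. The point is worth correcting because it concerns a harm that the protocol names and because the correction is cheap.

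**What to change.** - Reconcile the relatedness scope of 8.4.1, 8.4.2, 8.4.5 and 9.4.4 with that of 2.3.1, 8.4.3.2 and 8.4.4, so that events related to the study assessments are collected and reported. The requirement that a reaction be sustained, and the procedures for responding to distress, are not in question here.
- Keep the safety analysis set in 9.3 for the by-arm comparison of BRIGHT and AC.
- Add to 9.3 and 9.4.4 a listing and count of AEs from consent onward in all consented patients. Show events before randomization pooled, and events after randomization but before session 1 by assigned arm.

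The cost is a wording amendment, one additional safety table and slightly more event collection, since events due solely to a questionnaire are not now required under 8.4.5. The reported AE count may rise slightly. That would reflect the wider scope and should be stated when the results are reported.

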9.4 STATISTICAL ANALYSES

A statistical analysis plan (SAP) will be developed prior to database lock. The SAP will detail all planned analyses and analytic methods.

All statistical analyses will be performed using SAS or R packages. Graphical displays (e.g., bar charts, boxplots) and summary statistics (e.g., mean, median, standard deviation, interquartile range) will be used to characterize the data. Two sample t-tests or non-parametric Wilcoxon rank-sum tests will be used to compare continuous measures. Normality and variance homogeneity assumptions will be assessed, with appropriate data transformations as needed. The chi-square test will be used to evaluate associations between discrete variables.

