3 OBJECTIVES AND ENDPOINTS

Table 5. Study Objectives and Endpoints	
OBJECTIVES	ENDPOINTS
Primary	
To evaluate the efficacy of BRIGHT compared with AC on HNC-related BID as measured by change from baseline in the IMAGE-HN score.	Change in the IMAGE-HN score from baseline to 6-months follow-up ^a
Secondary	
To evaluate the clinical response rate of BRIGHT compared with AC on HNC-related BID as measured by proportion of patients with a clinically meaningful change from baseline in the IMAGE-HN score.	Proportion of patients with a decrease in the IMAGE-HN score of ≥ 9 points from baseline
To further evaluate the short and longer-term efficacy of BRIGHT compared with AC on HNC-related BID as measured by change from baseline in the IMAGE-HN score.	Change in the IMAGE-HN score from baseline to 2-, 3-, and 9-month follow-up
To evaluate the efficacy of BRIGHT compared with AC on psychological and social well-being as measured by change from baseline in the Shame and Stigma Scale in HNC, PROMIS SF v1.0-Depression 8a, PROMIS SF v1.0-Anxiety 8a, Beck Scale for Suicidal Ideation, and PROMIS SF v2.0-Ability to Participate in Social Activities-8a scores.	Change in the Shame and Stigma in HNC score from baseline to 3-, 6-, and 9-month follow-up
	Change in the PROMIS SF v1.0-Depression 8a score from baseline to 3-, 6-, and 9-month follow-up
	Change in the PROMIS SF v1.0-Anxiety 8a score from baseline to 3-, 6-, and 9-month follow-up
	Change in the Beck Scale for Suicidal Ideation score from baseline to 3-, 6-, and 9-month follow-up
	Change in the PROMIS SF v2.0-Ability to Participate in Social Activities 8a score from baseline to 3-, 6-, and 9-month follow-up
To evaluate the efficacy of BRIGHT compared with AC on QOL as measured by change from baseline in the EORTC QLQ-HN35 score.	Change in the EORTC QLQ-HN35 Trouble with Social Eating and Trouble with Social Contract subscale scores from baseline to 3-, 6-, and 9-month follow-up

Table 5. Study Objectives and Endpoints	
OBJECTIVES	ENDPOINTS
To examine the mechanism of change underlying BRIGHT for HNC-related BID as measured by change from baseline in the Body Image Coping Strategies Inventory (BICSI) subscale scores and Automatic Thoughts Questionnaire scores.	Change in the BICSI Avoidance subscale score from baseline to 2-, 3-, and 6-month follow-up
	Change in the BICSI Positive Rational Acceptance subscale score from baseline to 2-, 3-, and 6-month follow-up

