9.4.3 ANALYSIS OF SECONDARY ENDPOINTS

Secondary endpoints for changes in stigma, depression, anxiety, suicidal ideation, social isolation, and QOL will be analyzed with similar approaches. Covariates prognostic for each of these secondary endpoints will be pre-specified prior to formulation of the final SAP.

We will perform a causal mediation analysis¹⁰⁵ to evaluate the degree to which the effect of treatment (BRIGHT) on the primary outcome (change in IMAGE-HN scores between baseline and 6-month follow-

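### The response-rate endpoint has no clustered analysis, and the only stated test that fits it is a chi-square that treats patients as independent

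*Protocol*

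**What the plan says.** - **Clustering.** Protocol 9.2 states that the sample size "requires adjusting for the clustering of trial participants within psychologist" (BRIGHT) or clinical staff member (attention control). It plans on 9 clusters per arm, 10 patients per cluster and an ICC of 0.05. Section 9.4.2 gives this clustering as the reason for GEE, with an identity link, exchangeable working correlation and robust variance, applied to change in IMAGE-HN.
- **General rule.** The opening of 9.4 says: "Two sample t-tests or non-parametric Wilcoxon rank-sum tests will be used to compare continuous measures". It continues: "The chi-square test will be used to evaluate associations between discrete variables". Neither sentence is limited to baseline or descriptive use. The same opening leaves full detail to a SAP.
- **Secondary endpoints.** Section 9.4.3 says: "Secondary endpoints for changes in stigma, depression, anxiety, suicidal ideation, social isolation, and QOL will be analyzed with similar approaches".
- **Response.** Table 5 lists, against the first secondary objective, "Proportion of patients with a decrease in the IMAGE-HN score of ≥ 9 points from baseline". The synopsis places it at 3, 6 and 9 months. It is not in the 9.4.3 list.
- **Mechanism scores.** Section 9.4.3 gives the three BICSI subscales and the Automatic Thoughts Questionnaire structural equation mediation models. A multilevel version is used only if the cluster effect proves significant.

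**The concern.** BRIGHT is given by psychologists and attention control by head and neck clinical staff, so each interventionist works in one arm only. Any correlation among patients of the same interventionist then inflates the variance of the between-arm difference. A chi-square test ignores this, so its standard error is too small and it rejects a true null too often. It also drops the baseline and stratification adjustment used for the primary endpoint.

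The gap falls on response because no later section overrides the general rule for it. A SAP author who follows section 9.4 as written would test the first secondary objective by a method that conflicts with 9.2 and 9.4.2. For the mechanism scores the issue is different: clustering is recognised, but accounted for only after a preliminary test that will often miss it.

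**Working it through.** **Inputs from Protocol 9.2:** two-sided 5% level; difference 9; SD 16; ICC 0.05; 9 clusters of 10 per arm (90 per arm). **Assumptions, because the protocol gives no figure:** response rates of 30% and 50%, equal in both arms under the null; the binary-scale ICC; the form of the test for a cluster effect; and the use of ICC 0.05 for the mechanism scores.

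**1. The plan's own figure.** Section 9.2 says: "We target a mean difference in IMAGE-HN score reduction of 9 between BRIGHT and AC at 6 months".
- Design effect = 1 + (10 − 1) × 0.05 = 1.45.
- SE = 16 × √(2 × 1.45 / 90) = 2.872.
- Non-centrality = 9 / 2.872 = 3.134, with 2 × (9 − 1) = 16 degrees of freedom.
- Power = 83.67%.

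This matches the statement that the sample "yields 83.7% power to detect the targeted 9-point average reduction in IMAGE-HN scores". Ignoring clustering would give 96.5%, so the planning depends on accounting for it.

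**2. Error of an unclustered test.** Under the null the naive z statistic has variance equal to the design effect (DE), so the true error is 2 × [1 − Φ(1.96 / √DE)]. At a binary-scale ICC of 0.05 and 10 per cluster this is 2 × [1 − Φ(1.96 / 1.204)] = 10.4%. A beta-binomial simulation with 40% response gave 10.9%.

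**3. Response dichotomised from a score with ICC 0.05.** Cutting a continuous score weakens the within-cluster correlation. The binary ICC is (P11 − p²) / [p(1 − p)], where P11 is the probability that two patients of one interventionist both respond, from a bivariate normal with correlation 0.05.

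| Response rate | Binary ICC | Design effect | Error by formula | Simulated chi-square | Simulated, continuity-corrected |
|---|---|---|---|---|---|
| 30% | 0.029 | 1.261 | 8.1% | 7.9% | 5.8% |
| 50% | 0.032 | 1.287 | 8.4% | 7.9% | 5.9% |

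(20,000 simulated null trials, 9 clusters of 10 per arm.)

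**4. Sensitivity to the binary-scale ICC, by the formula in step 2.** 0.01: 6.1%; 0.02: 7.1%; 0.03: 8.2%; 0.05: 10.4%; 0.10: 15.5%.

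**5. The significance trigger for the mechanism scores.** Take a one-way F-test for interventionist within arm, with 16 and 162 degrees of freedom.
- The expected ratio of mean squares is 1 + 10 × 0.05 / 0.95 = 1.526.
- The 5% critical value is 1.706.
- Power = P(F > 1.706 / 1.526) = P(F > 1.118) = about 34%.

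At the planning ICC the unclustered version would be used about two times in three.

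**The case against.** The strongest reply is that the opening of 9.4 is boilerplate. It leaves detail to the SAP and names no endpoint. Its t-test sentence, read as literally, would also govern the primary endpoint, which 9.4.2 plainly assigns to GEE. The pilot reported a model-based odds ratio for this same response definition (2.2.10), which suggests that the team would model it again.

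Part of this stands. A reader might infer that the protocol chose chi-square for response; it does not say so. But for the primary endpoint a later section overrides the general rule, and for response none does. Section 9.3 also refers readers to 9.4 for the analytic plan of each population. The text therefore states an unrestricted rule that conflicts with the clustering requirement, which is more than detail left to the SAP.

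Three stronger readings are not supported:
- **That every endpoint outside the 9.4.3 list is left to a t-test.** IMAGE-HN change at the other timepoints has GEE and mixed models in 9.4.2, and the BICSI and Automatic Thoughts scores have mediation models in 9.4.3.
- **That the point extends to alliance, empathy and expectancy.** These are not Table 5 endpoints, and the protocol states no between-arm hypothesis for them.
- **That the error rate for response doubles.** That needs a binary-scale ICC of about 0.05. The 0.05 in 9.2 was set for the IMAGE-HN score, and dichotomising such a score brings it down to about 0.03.

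**Conclusion.** The point holds for response, conditional on the stated chi-square being used. Its true type I error would then be about 8% against a nominal 5%, about 6% with continuity correction, and about 10–11% if the binary-scale ICC is itself 0.05. These figures rest on 9 clusters of 10 per arm and on assumed response rates. The primary analysis is not affected.

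For the BICSI and Automatic Thoughts scores a method is stated, but making the clustered version depend on a significant cluster effect is a weak safeguard, with about 34% power at ICC 0.05.

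**What to change.** - **Section 9.4:** limit the t, Wilcoxon and chi-square tests to descriptive use.
- **Section 9.4.3, response:** state that response is analysed with a binary GEE clustered on interventionist and adjusted for site, free flap reconstruction and baseline IMAGE-HN, reporting an odds ratio or risk difference.
- **Section 9.4.3, mechanism scores:** state that between-arm comparisons of the BICSI subscales and the Automatic Thoughts score use the clustered model whatever the result of a test for a cluster effect.

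The cost is a few sentences and slightly wider confidence intervals. No data collection or sample size changes.
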